8.3.3 Protocol Amendment and/or Revision

Any changes to the study that arise after approval of the protocol must be documented as protocol amendments: substantial amendments and/or administrative changes/non-substantial amendments. Depending on the nature of the amendment and/or administrative change, either IRB/IEC approval or notification is required. The changes will become effective only after the approval of the sponsor, the investigator, the regulatory authority, and the IRB/IEC (if applicable).

Amendments to this protocol must be signed by the sponsor and the investigator. Written verification of IRB/IEC approval will be obtained before any amendment is implemented which affects subject safety or the evaluation of safety, and/or efficacy. Modifications to the protocol that are administrative in nature do not require IRB/IEC approval, but will be submitted to the IRB/IEC for their information, if required by local/national regulation.

8.3.4 Insurance of Subjects and Others

The sponsor, Astellas Pharma Europe B.V., has covered this study by means of an insurance of the study according to national requirements. The name and address of the relevant insurance company, the certificate of insurance, the policy number and the sum insured are provided in the Investigator's File.

8.3.5 Investigator Indemnity

The sponsor agrees to, and does hereby, indemnify, defend and hold the investigator harmless from and against all claims, demands, actions, and proceedings which may be brought or asserted against the investigator to recover damages and losses for or attributable to bodily injury, sickness, disease, or death arising from or alleged to arise from or be reasonably attributable to this study.

Notwithstanding the foregoing, the sponsor does not, however, agree to indemnify, defend or hold the investigator harmless from claims, demands, actions, proceedings or damages resulting or claimed to have resulted from:

- Failure of the investigator to evaluate or properly interpret available information that is relevant to this study, and for independent decisions made as the result of such failure;
- Failure of the investigator to adhere to all provisions of the protocol for this study and to written recommendations and written instructions delivered to the investigator by the sponsor concerning the administration and use of drug substances, including the placebo, involved in this study;
- Failure of the investigator to render professional service or to conduct this study in a normal, prudent manner.

A condition of this indemnity obligation is that, whenever the investigator has information from which it may be reasonably concluded that an incident of bodily injury, sickness, disease or death has occurred, the investigator shall immediately give notice to the sponsor of all pertinent data surrounding any such incident, and, in the event a claim is made or a suit is brought, the investigator shall assist the sponsor and cooperate in the gathering of information with respect to the time, place, and circumstances and in obtaining the names and addresses of the injured parties and available witnesses. The investigator shall not, except at his own cost, voluntarily make any payment or incur any expense in connection with any such claim or suit without the prior written consent of the sponsor.

8.3.6 Signatory Investigator for Clinical Study Report

ICH E3 guidelines recommend and EU Directive 2001/83/EC requires that a final study report which forms part of a marketing authorization application be signed by the representative for the Coordinating Investigator(s) or the Principal Investigator(s). The representative for the Coordinating Investigator(s) or the Principal Investigator(s) will have the responsibility to review the final study results to confirm to the best of his/her knowledge it accurately describes the conduct and results of the study. The representative for Coordinating Investigator(s) or the Principal Investigator(s) will be selected from the participating investigators by the Sponsor prior to database lock.

9 QUALITY ASSURANCE

The sponsor is implementing and maintaining quality assurance and quality control systems with written SOPs to ensure that trials are conducted and data are generated, documented (record), and reported in compliance with the protocol, GCP, and applicable regulatory requirement(s).

The sponsor or sponsor's designee may arrange to inspect/audit the clinical study at any or all investigational sites. The auditor is independent from the clinical monitoring and project management team at the sponsor. The audit may include on-site review of regulatory documents, case report forms, and source documents. Direct access to these documents will be required by the auditors.

10 STUDY ORGANIZATION

10.1 Data Monitoring Committee

Not applicable.

10.2 Other Evaluation Committee(s)

Not applicable.

10.3 Other Study Organization

Not applicable.

12 APPENDICES

12.1 Appendix 1: Laboratory Tests

Test type	Visit	Parameters to be analyzed
Hematology	All visits	Hemoglobin (Hgb) Hematocrit (HCT) Complete Cell Count (CBC) Red Blood Cells (RBC) White blood cells (WBC) Differential WBC Platelets
Biochemistry	All visits	sodium potassium calcium chloride magnesium phosphate glucose creatinine alkaline phosphatase alanine aminotransferase (ALT) aspartate aminotransferase (AST) gamma-glutamyl transferase (GGT) total bilirubin total protein albumin bicarbonate (CO ₂) blood urea nitrogen (BUN)

12.2 Appendix 2: Liver Safety Monitoring and Assessment

If laboratory testing for a subject enrolled in study and receiving study drug reveals an increase of serum aminotransferases (AT) to $> 3X$ ULN, or bilirubin $> 2X$ ULN, at least all four of the usual serum hepatic measures (ALT, AST, ALP, and bilirubin [TBL]) should be repeated. Testing should be repeated within 48-72 hours of notification of the test results. For studies for which a central laboratory is used, alerts will be generated by the central lab regarding moderate and marked liver abnormality to inform the investigator, study monitor and study team. Subjects should be asked if they have any symptoms suggestive of hepatobiliary dysfunction.

Definition of Liver Abnormalities

Confirmed abnormalities will be characterized as moderate and marked where ULN:

Moderate	ALT or AST $> 3 \times \text{ULN}$	or	Total Bilirubin $> 2 \times \text{ULN}$
Marked	$> 3 \times \text{ULN}$	and	$> 2 \times \text{ULN}$

In addition, the subject should be considered to have marked hepatic abnormalities for any of the following:

- ALT or AST $> 8X$ ULN
- ALT or AST $> 5X$ ULN for more than 2 weeks
- ALT or AST $> 3X$ ULN and INR > 1.5
- ALT or AST $> 3X$ ULN with the appearance of fatigue, nausea, vomiting, right upper quadrant pain or tenderness, fever, rash and/or eosinophilia ($> 5\%$).

The investigator may determine that abnormal liver function results, other than as described above, may qualify as moderate or marked abnormalities and require additional monitoring and follow-up. Discontinuation of treatment must occur if subject has marked abnormalities. In addition, if closed monitoring for a subject with moderate hepatic laboratory tests is not possible, drug should be discontinued.

Follow-up Procedures

Confirmed moderate and marked abnormalities in hepatic functions should be thoroughly characterized by obtaining appropriate expert consultations, detailed pertinent history, physical examination and laboratory tests. The site should complete the Liver Abnormality Case Report Form (LA-CRF) or an appropriate document. Subjects with confirmed abnormal liver function testing should be followed as described below.

Confirmed moderately abnormal liver function tests (LFTs) should be repeated 2-3 times weekly then weekly or less if abnormalities stabilize or the study drug has been discontinued and the subject is asymptomatic.

Marked hepatic liver function abnormalities, in the absence of another etiology, may be considered an important medical event and reported as a Serious Adverse Event (SAE). The

sponsor should be contacted and informed of all subjects for whom marked hepatic liver function abnormalities possibly attributable to study drug are observed.

To further assess abnormal hepatic laboratory findings, the investigator is expected to:

- Obtain a more detailed history of symptoms and prior or concurrent diseases. Symptoms and new onset-diseases should be recorded as 'adverse events' on the AE page of eCRF. Illnesses and conditions such as hypotensive events, and decompensated cardiac disease that may lead to secondary liver abnormalities should be noted. Non-alcoholic steatohepatitis (NASH) is seen in obese hyperlipoproteinemic, and/or diabetic patients and may be associated with fluctuating aminotransferase levels. The investigator should ensure that the medical history form captures any illness that pre-dates study enrollment that may be relevant in assessing hepatic function.
- Obtain a history of concomitant drug use (including non-prescription medication, complementary and alternative medications), alcohol use, recreational drug use, and special diets. Medications, including dose, should be entered on the concomitant medication page of eCRF. Information on alcohol, other substance use, and diet should be entered on the LA-CRF or an appropriate document.
- Obtain a history of exposure to environmental chemical agents
- Based on the subject's history, other testing may be appropriate including:
 - acute viral hepatitis (A,B, C, D, E or other infectious agents)
 - ultrasound or other imaging to assess biliary tract disease
 - other laboratory tests including INR, direct bilirubin.
- Consider gastroenterology or hepatology consultations.
- Submit results for any additional testing and possible etiology on the LA-CRF or an appropriate document.

Study Discontinuation

In the absence of an explanation for increased LFTs, such as viral hepatitis, pre-existing or acute liver disease or exposure to other agents associated with liver injury, the subject may be discontinued from the study. The investigator may determine that it is not in the subject's best interest to continue study enrollment.

Discontinuation of treatment must occur if:

- ALT or AST > 8X ULN
- ALT or AST > 5X ULN for more than 2 weeks
- ALT or AST > 3X ULN and (TBL > 2X ULN or INR > 1.5)

Discontinuation of treatment should be considered if:

- ALT or AST > 3X ULN with the appearance of fatigue, nausea, vomiting, right upper quadrant pain or tenderness, fever, rash and/or eosinophilia (> 5%).

In addition, if close monitoring for a subject with moderate or marked hepatic laboratory tests is not possible, drug should be discontinued.

Reference

Guidance for Industry titled “Drug-Induced Liver Injury: Premarketing Clinical Evaluation” issued by FDA on July 2009.

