5.4 Safety Assessment

Please review the requirements related to the evaluation, reporting and analysis of Drug-Induced Liver Injury (DILI) information found in [Appendix 2](#) (Liver Safety Monitoring and Assessment). In the event of a confirmed, marked hepatic abnormality as defined in [Appendix 2](#) (Liver Safety Monitoring and Assessment), it is the investigator's responsibility to ensure contact with the sponsor/delegated CRO by telephone or fax immediately (i.e. within 24 hours of awareness).

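### Appendix 2 both requires and merely suggests stopping drug for one of its five listed marked liver criteria: ALT or AST above 3x ULN with symptoms or eosinophilia

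*Protocol*

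**What the plan says.** Protocol Appendix 2 deals with stopping drug for liver findings in two places.

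The first is the part that defines liver abnormalities. A table row calls ALT or AST above 3x ULN together with total bilirubin above 2x ULN marked. The text then adds that "the subject should be considered to have marked hepatic abnormalities for any of the following", followed by four bullets. The last bullet is ALT or AST above 3x ULN accompanied by any of seven features: fever, rash, fatigue, nausea, vomiting, right upper quadrant pain or tenderness, or eosinophilia above 5%. The next paragraph sets the action: "Discontinuation of treatment must occur if subject has marked abnormalities". It continues: "if closed monitoring for a subject with moderate hepatic laboratory tests is not possible, drug should be discontinued".

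The second is the Study Discontinuation part. Its must-stop list has three items and does not contain the symptom criterion. That criterion, in the same terms, is the only item under "Discontinuation of treatment should be considered if". The closing sentence there reads: "if close monitoring for a subject with moderate or marked hepatic laboratory tests is not possible, drug should be discontinued".

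**The concern.** The same laboratory and clinical picture gets *must* in one place and *should be considered* in the other. The close-monitoring sentences split along the same line. The first names moderate cases only, which fits a rule that every marked case stops. The second names moderate or marked cases, which presumes that some marked cases stay on drug.

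This is a patient-safety stopping rule, and each site applies it alone. Laboratory work is local (Protocol 5.4.3 and 8.1.1), so the central-laboratory alerts described in Appendix 2 do not apply, and there is no data monitoring committee (10.1). A site that reads only the Study Discontinuation part could keep a subject with a marked abnormality on drug. The retest schedule of 2-3 times weekly is written for moderately abnormal tests, so it is unclear whether it reaches a subject classed as marked who stays on drug. Routine visits are 12 weeks apart up to week 85 and 24 weeks apart after that (Table 1).

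There is also a small reporting effect. Deviation PD2 counts subjects who developed withdrawal criteria and were not withdrawn (Protocol 7.7 and 8.1.6; SAP 7.2.2). A symptomatic subject kept on drug would be scored under the first rule and not under the second.

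**Working it through.** The plan gives no figure to reproduce. The check sets each listed marked criterion against both parts of Appendix 2.

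| Listed marked criterion | Definitions part | Study Discontinuation part |
|---|---|---|
| ALT/AST >3x ULN and bilirubin >2x ULN | must | must |
| ALT/AST >8x ULN | must | must |
| ALT/AST >5x ULN for more than 2 weeks | must | must |
| ALT/AST >3x ULN and INR >1.5 | must | must |
| ALT/AST >3x ULN with a listed feature | must | consider |

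**Count.** One table row + 4 bullets = 5 listed criteria. The must-stop list has 3 items; its third joins the bilirubin and INR criteria with *or*, so it covers 1 + 1 + 2 = 4 criteria. The remainder is 5 - 4 = 1, the symptom criterion.

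**Who falls in the conflict.** A subject must meet the symptom criterion and none of the must-stop items. Removing each item in turn leaves:
- ALT or AST above 3x ULN (the criterion itself) and at most 8x ULN (first item not met);
- not above 5x ULN for more than 2 weeks (second item not met);
- bilirubin at most 2x ULN, and INR at most 1.5 or not measured (third item not met);
- at least one of the seven features.

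The unmeasured case is realistic. INR is not in the routine panel (5.4.3.3 and Appendix 1); Appendix 2 mentions it only as a further test that may be appropriate.

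**Does another section settle it?** Sections 3.4 and 6.1 contain no liver stopping rule. Section 5.1.2 covers interruption for grade 3 or greater toxicity in general. Sections 5.4 and 5.4.3.1 refer back to Appendix 2. None says which line prevails. Both lines are current text, not amendment-log text.

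**How many subjects?** This cannot be calculated. The documents give no rate of ALT or AST above 3x ULN and no planned number of subjects (7.1).

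**The case against.** **The specific line overrides the general one.** This fails. The definitions part also names the symptom criterion specifically, and no order of precedence is stated.

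**Mandatory if confirmed, discretionary if not.** Appendix 2 does characterise abnormalities once confirmed, but neither the *must* sentence nor the two lists draws that distinction.

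**There is a safe common action.** This stands. Stopping drug satisfies both lines. Tests are repeated within 48-72 hours, confirmed moderate and marked cases call for expert consultation, and a confirmed marked case requires sponsor contact within 24 hours (5.4). The text gives the sponsor no rule for settling the conflict, but the case would be seen.

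**Three stronger readings are tempting, and the documents do not support them.**
- A reader might infer that two sites could both comply fully while acting in opposite ways. They could not: the site that continues drug breaches an unqualified *must*. The fault is text that invites a breach.
- A reader might infer a second contradiction from "The investigator may determine that abnormal liver function results, other than as described above, may qualify as moderate or marked abnormalities", because the must-stop list does not mention such cases. That list does not claim to be exhaustive, and the general *must* still covers them.
- A reader might infer that the conflict will arise often because fatigue, nausea and vomiting appear among the common serious events in Appendix 3. That is only 3 of the 7 features, and the frequency of a symptom alone does not show how often it accompanies ALT or AST above 3x ULN.

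**Conclusion.** The text is wrong as written: an internal inconsistency in 1 of 5 listed marked criteria, with the other 4 consistent. It rests on the protocol wording alone and needs no outside assumption.

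Severity is minor. The primary safety endpoints and the analysis set are unaffected; the only tabulated result exposed is the PD2 count, and that effect is descriptive. The number of affected subjects is unknown. The sponsor is closing the study (Synopsis and 5.1.1; planned end 1Q2017), so the conflict matters only while subjects remain on drug in it.

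**What to change.** Keep one rule.

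**Preferred, because it follows the unqualified *must*:** add the symptom criterion to the must-stop list under Study Discontinuation, delete the discretionary item, and limit the closing close-monitoring sentence to moderate cases.

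**If the sponsor intends discretion:** exempt this criterion expressly from the *must* sentence in the definitions part, state that retesting 2-3 times weekly applies to such a subject kept on drug, and make the two close-monitoring sentences agree.

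The choice is a clinical one for the sponsor. Either way, PD2 can then be scored against a single rule.

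**Cost:** a few lines, with no added procedures or subjects. Because the change affects subject safety, IRB/IEC approval is needed before implementation (8.3.3), and it helps only if it takes effect before subjects leave the study. The preferred option may make some subjects stop a drug judged to benefit them; the alternative lets a subject with a marked abnormality stay on drug.

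### Appendix 2 makes stopping treatment both mandatory and discretionary for a confirmed ALT or AST above 3X ULN with symptoms and no other marked criterion

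*Protocol*

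**What the plan says.** Protocol Appendix 2 (Section 12.2) states the liver stopping rule twice.

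Under Definition of Liver Abnormalities, "Confirmed abnormalities will be characterized as moderate and marked". A table row makes ALT or AST above 3X ULN together with total bilirubin above 2X ULN marked. Then "the subject should be considered to have marked hepatic abnormalities for any of the following", followed by four further criteria. The fourth is "ALT or AST > 3X ULN with the appearance of fatigue, nausea, vomiting, right upper quadrant pain or tenderness, fever, rash and/or eosinophilia" (above 5%), with no bilirubin or INR condition attached. The action follows without exception: "Discontinuation of treatment must occur if subject has marked abnormalities". The next sentence there requires stopping when close monitoring is not possible, and it covers moderate cases only.

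Under Study Discontinuation, the heading "Discontinuation of treatment must occur if" introduces three items: above 8X ULN; above 5X ULN for more than 2 weeks; and above 3X ULN with either bilirubin above 2X ULN or INR above 1.5. The symptom criterion is not among them. It appears next, in the same words, under "Discontinuation of treatment should be considered if". The closing sentence reads "if close monitoring for a subject with moderate or marked hepatic laboratory tests is not possible, drug should be discontinued".

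**The concern.** This is the stopping rule for possible drug-induced liver injury with symptoms. For one confirmed result it supports a mandatory stop in one place and a judgement call in another. An investigator who keeps dosing follows the Study Discontinuation text and breaches the definition text.

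Four features of the study make the ambiguity matter in practice.

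- The triggering symptoms are common in these patients. Asthenia/fatigue is among the most common adverse reactions in Section 1.3. Asthenia/fatigue, nausea and vomiting are in Appendix 3, the list of serious events that Section 5.5.8 anticipates whether or not drug is given. Attribution will often be a genuine judgement, so the protocol has to say whether that judgement is allowed.
- Laboratory tests are local (Sections 5.4.3 and 8.1.1), so the central-laboratory alerts mentioned in Appendix 2 do not apply. There is no data monitoring committee (Section 10.1).
- Appendix 2 gives a retest frequency (2-3 times weekly at first) only for moderate abnormalities. A marked subject kept on drug has no stated schedule, and from week 85 routine visits are 24 weeks apart (Table 1).
- Section 5.4 requires sponsor contact within 24 hours for a confirmed marked abnormality, but does not say which rule then applies.

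**Working it through.** No arithmetic applies, so the check is a comparison of the two statements.

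1. *Same finding and same action?* Yes. The symptom criterion is worded identically in both places. Although the second part is headed Study Discontinuation, both rules concern discontinuation of treatment, so a distinction between leaving treatment and leaving the study does not reconcile them.

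2. *Same status?* Yes. Both are current text. The Amendment 4 changes shown do not touch Appendix 2.

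3. *Criterion by criterion:*

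| Stated marked criterion (ALT or AST) | Definition text | Study Discontinuation text |
|---|---|---|
| > 3X ULN and bilirubin > 2X ULN | must stop | must stop |
| > 8X ULN | must stop | must stop |
| > 5X ULN for more than 2 weeks | must stop | must stop |
| > 3X ULN and INR > 1.5 | must stop | must stop |
| > 3X ULN with symptoms or eosinophilia > 5%, nothing else met | must stop | consider stopping |

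Four of the five agree; one conflicts.

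4. *Boundaries of the conflict.* A subject who also meets another marked criterion must stop under both parts. What remains is a confirmed, symptomatic case with bilirubin not above 2X ULN, INR not above 1.5 or not measured, and ALT or AST either above 3X up to 5X ULN for any duration, or above 5X up to 8X ULN for no more than 2 weeks. The unmeasured case belongs here because INR is not in the scheduled panel (Section 5.4.3.3, Appendix 1); Appendix 2 mentions it only among further tests that may be appropriate.

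5. *Monitoring sentences.* The first covers moderate cases, which fits a rule under which every marked subject has already stopped. The second covers moderate or marked cases, which makes sense only if some marked subjects are still on drug. The two sentences differ in the same direction as the two rules.

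6. *Precedence.* None is stated. Sections 5.4 and 5.4.3.1 refer the reader to Appendix 2, and Section 3.4 has no liver-specific rule. The statement that a subject should be considered to have marked abnormalities governs classification; it does not soften the mandatory sentence about action.

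**The case against.** The best reply is that the conflict runs one way. Stopping satisfies both parts, and the later text never expressly authorises continued dosing. A reader might infer that the appendix permits a site to carry on; that goes too far. What the documents support is that discretion is offered in one place and withdrawn in another. The cautious reader is safe, but one who turns to the section actually headed for discontinuation finds only discretion for this finding.

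A reconciliation is possible: stopping is considered at the first result and becomes mandatory on confirmation, since the definition speaks of confirmed abnormalities and the later lists do not. This is strained. The later part never draws that line, its own mandatory items carry no confirmation condition, and its closing sentence treats marked subjects as possibly still on drug.

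Discretion may also be what the sponsor intends, because the later part deliberately separates mandatory from discretionary stops. That stands, and it is why the fix offers both directions.

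The practical consequences are limited. Each confirmed marked case should reach the sponsor within 24 hours, the investigator may end a subject's involvement when his condition warrants it (Section 3.4), and the study is being closed (Section 5.1.1). These points reduce the risk of unnoticed divergence between sites, but they do not say which rule applies to subjects still on drug.

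**Conclusion.** The contradiction is real and confined to one criterion: a confirmed ALT or AST above 3X ULN with the listed symptoms or eosinophilia and no other marked criterion met. It should be corrected because it concerns a patient-safety stopping rule. The conclusion rests on the printed text alone and needs no assumption about event rates.

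Three wider inferences are not supported.

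- A reader might conclude that the liver stopping rules are unreliable throughout. The other four stated criteria agree. Cases that the investigator classes as marked on other grounds are missing from the later lists, but the earlier mandatory sentence already covers them; that is an omission, not a contradiction.
- A reader might want to call the situation rare or frequent. The documents give no basis for either.
- A reader might expect the protocol-deviation tables to be distorted. The category for subjects who met withdrawal criteria but stayed on is not defined by reference to Appendix 2, so that question would remain open even if the appendix were consistent. No planned analysis is shown to change.

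**What to change.** In the Study Discontinuation part of Appendix 2:

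1. Keep the three existing mandatory items exactly as they are. Do not replace them with a general rule for confirmed marked abnormalities: they carry no confirmation condition now, and adding one could delay an existing stop (for example above 8X ULN) until the repeat test, due 48-72 hours after notification.
2. Add a fourth mandatory item: confirmed ALT or AST above 3X ULN with any of the listed symptoms and/or eosinophilia above 5%. Keep the discretionary wording for the same finding before confirmation.
3. In the closing monitoring sentence, change *moderate or marked* to *moderate*, to match the definition part.

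If the sponsor wants discretion for this criterion, exempt it instead from the mandatory sentence in the definition part, and state a retest schedule for such subjects while they stay on drug.

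The mandatory version has a clinical cost: a subject with a confirmed elevation whose fatigue or nausea comes from his cancer would have to stop. It needs no new test or visit; the discretionary version adds the retests that its schedule specifies. Either version is a few sentences of text, but because it affects subject safety it needs an amendment signed by sponsor and investigator, with IRB/IEC approval before implementation (Section 8.3.3).
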